10 JUL 2023

Date

PROTOCOL VERSION 4.0 SUMMARY OF CHANGES TABLE

Document History	
Document:	Date (Day-Month-Year)
Version 4.0	06 Jul 2023
Version 3.0	03 Sep 2021
Version 2.0	29 Jun 2020
Original Protocol Version 1.0	07 Oct 2019

Amendment: Protocol Version 4.0 (06 Jul 2023)

This amendment is considered to be substantial based on the criteria set forth in Article 10(a) of Directive 2001/20/EC of the European Parliament and the Council of the European Union.

Overall Rationale for the Amendment: The overall rationale for this amendment is to add eye examinations as an additional trial assessment to monitor for the new potential risk of increased intraocular pressure across the Phase 3 tavapadon protocols.

Section # and Name	Description of Change	Brief Rationale
1.3 Schedule of Assessments	Added eye examination assessment Added footnotes “v” and “w” to clarify the assessment and follow-up frequency Removed footnote “b” allowing remote visits if the subject cannot attend the clinic visit in person due to restrictions related to COVID-19 Note, footnote order has shifted as a result of these changes.	To monitor for increased intraocular pressure Remote visits are no longer needed as COVID-19 restrictions have ended
7.3 Individual Subject Discontinuation	Removed reference to in-home visits	Remote visits are no longer needed as COVID-19 restrictions have ended
8.3.8 Eye Examinations	Added new section for eye examinations and guidance for follow-up	To monitor for increased intraocular pressure

TABLE OF CONTENTS

PROTOCOL VERSION 4.0 SUMMARY OF CHANGES TABLE	3
TABLE OF CONTENTS	4
TABLE OF TABLES.....	7
TABLE OF FIGURES.....	7
1 PROTOCOL SUMMARY	8
1.1 Synopsis.....	8
1.2 Schema	12
1.3 Schedule of Assessments.....	12
2 INTRODUCTION	17
2.1 Trial Rationale	17
2.2 Background	17
2.3 Benefit/Risk Assessment.....	19
3 OBJECTIVES AND ENDPOINTS.....	21
4 TRIAL DESIGN	22
4.1 Overall Design	22
4.1.1 Screening/Baseline Period.....	22
4.1.2 Treatment Period	23
4.1.3 Safety Follow-up Period	24
4.1.4 Concentration-QT Substudy.....	24
4.2 Scientific Rationale for Trial Design.....	24
4.3 Justification for Dose	25
4.4 Definition of Completed Subject.....	26
4.5 End of Trial Definition	26
5 TRIAL POPULATION	26
5.1 Inclusion Criteria	26
5.2 Exclusion Criteria	27
5.3 Lifestyle Considerations	30
5.4 Screen Failures	30
6 TRIAL TREATMENTS.....	30
6.1 Trial Intervention(s) Administered	30
6.2 Preparation/Handling/Storage/Accountability	31

1 PROTOCOL SUMMARY

1.1 Synopsis

Sponsor Name: Cerevel Therapeutics, LLC

Name of Investigational Medicinal Product: Tavapadon

Protocol Title: A Phase 3, Double-Blind, Randomized, Placebo-Controlled, Parallel-Group, 27-Week Trial to Evaluate the Efficacy, Safety, and Tolerability of Two Fixed Doses of Tavapadon in Early Parkinson's Disease (TEMPO-1 Trial)

Short Title: Fixed-Dose Trial in Early Parkinson's Disease

IND Number: 118,647

EudraCT Number: 2019-002949-38

Trial Phase: 3

Indication: Parkinson's disease

Rationale: Tavapadon (PF-06649751, CVL-751) is a partial agonist of the dopamine D1-like receptors (D1Rs), with high specificity for the D1 and D5 receptor subtypes (D1/D5), which is being developed as a treatment for Parkinson's disease (PD). The efficacy, safety, and tolerability of tavapadon in Phase 1b and 2 trials support its potential as the first partial agonist therapy in an important new dopamine receptor-selective mechanism for treatment of PD symptoms. By targeting the D1R subtype, tavapadon aims to improve motor control symptoms while minimizing adverse events (AEs) that may be mechanistically linked to D2/D3 dopamine receptor agonists (notably, dose-limiting hypotension, impulse control disorders, sleep disorders, and, potentially, some forms of hallucinations). This trial is designed to further define and confirm the magnitude of efficacy and the risk/benefit profile of tavapadon over the target dose range of 5 to 15 mg once daily (QD).

Objectives and Endpoints:

The objectives and efficacy, safety, and pharmacokinetic (PK) endpoints of the trial are summarized in [Table 1](#).

Table 1 Objectives and Endpoints

Objectives	Endpoints
Primary	
Primary Efficacy Endpoint
 
 • To assess the efficacy of 2 fixed doses of tavapadon in subjects with early PD 
Key Secondary Efficacy Endpoints
 
 • Change from baseline to endpoint in the MDS-UPDRS Part II score • Percentage of responders at endpoint, defined as a score of “much improved” or “very much improved” on the PGIC 
Secondary Efficacy Endpoints (All Time Points)
 
 • Change from baseline in the MDS-UPDRS Parts II and III combined score • Change from baseline in the MDS-UPDRS Parts I, II, and III combined score • Change from baseline in the MDS-UPDRS Part I, Part II, and Part III individual scores • Change from baseline in the CGI-S score • CGI-I score • PGIC score 
Other Endpoints
 
 • Change from baseline in PDQ-39 score • Change from baseline in Schwab and England ADL score • Change from baseline in the EQ-5D-5L index and VAS scores
Secondary	
 • To assess the safety and tolerability of 2 fixed doses of tavapadon in subjects with early PD
Pharmacokinetic	
 • ESS • QUIP-RS • C-SSRS • Nature, frequency, and temporality of TEAEs, including abuse-related AEs and AEs related to MHIs • Clinical laboratory evaluations • Vital signs • Physical and neurological examinations • ECGs
	
 • Plasma concentrations of tavapadon and its major metabolite (if required) at baseline (Day 1) and Weeks 5, 11, 14, 22, and 27

Abbreviations: ADL = activities of daily living, AE = adverse event, CGI-I = Clinical Global Impression – Improvement, CGI-S = Clinical Global Impression – Severity of Illness, C-SSRS = Columbia-Suicide Severity Rating Scale, ECG = electrocardiogram, EQ-5D-5L = EuroQol 5 Dimension 5 Level, ESS = Epworth Sleepiness Scale, MDS-UPDRS = Movement Disorder Society-Unified Parkinson’s Disease Rating Scale, MHIs = medication handling irregularities, PD = Parkinson’s disease, PDQ-39 = 39-Item Parkinson’s Disease Rating Scale, PGIC = Patient Global Impression of Change, PK = pharmacokinetic, QUIP-RS = Questionnaire for Impulsive-Compulsive Disorders in Parkinson’s Disease-Rating Scale, TEAE = treatment-emergent adverse event, VAS = visual analog scale.

Overall Design:

This is a prospective, Phase 3, multicenter, multinational, randomized, double-blind, placebo-controlled, parallel-group, 27-week trial to evaluate the efficacy, safety, tolerability, and PK of 2 fixed doses of tavapadon (5 mg QD and 15 mg QD) in male and female subjects aged 40 to 80 years who have a diagnosis of PD (consistent with the UK Parkinson's Disease Society Brain Bank diagnostic criteria); a modified Hoehn and Yahr stage of 1, 1.5, or 2; a Movement Disorder Society – Unified Parkinson's Disease Rating Scale (MDS-UPDRS) Part II score ≥ 2 and Part III score ≥ 10 ; and are not receiving antiparkinsonian medication other than monoamine oxidase B (MAO-B) inhibitors. The trial will include a Screening Period (maximum of 4 weeks), a 27-week Treatment Period, and a 4-week Safety Follow-up Period.

Each subject will participate in the trial for up to approximately 35 weeks, including screening (up to 4 weeks), treatment (27 weeks), and posttreatment safety follow-up (4 weeks). Subjects who complete through Week 27 of the trial may have the opportunity to enter an open-label extension trial (Protocol CVL-751-PD-004).

A substudy to evaluate the effect of tavapadon on the QT interval using concentration-QT modelling is also included in this trial. Matched triplicate electrocardiograms (ECGs) and plasma tavapadon concentrations that are collected at preselected sites will be used to characterize the effects of tavapadon on the QT interval.

Disclosure Statement: This is a parallel-group trial to evaluate the efficacy, safety, tolerability, and PK of 2 fixed doses of tavapadon (5 mg QD and 15 mg QD) and placebo in subjects with early PD. Treatment assignments will be blinded to the investigators and other trial site personnel, the subjects, and all sponsor personnel who are involved in the conduct of the trial (including trial monitoring, data management, and data analysis).

Number of Subjects: A total of 522 subjects are planned to be randomized into 3 treatment groups (174 subjects per treatment group).

Key Entry Criteria: Male and female subjects aged 40 to 80 years who have a diagnosis of PD (consistent with the UK Parkinson's Disease Society Brain Bank diagnostic criteria); a modified Hoehn and Yahr stage of 1, 1.5, or 2; an MDS-UPDRS Part II score ≥ 2 and Part III score ≥ 10 ; and are not receiving antiparkinsonian medication other than MAO-B inhibitors will be enrolled.

Intervention Groups, Trial Treatments, and Duration: Subjects will be randomized in a 1:1:1 ratio to receive tavapadon 5 mg QD, tavapadon 15 mg QD, or placebo QD. The dose of tavapadon will be titrated to a target dose using a fixed titration scheme. Randomization will be stratified by concurrent use of allowed PD medications (MAO-B inhibitors) during the Treatment Period. The planned duration of treatment is 27 weeks, including the Titration, Adjustment, and Maintenance Phases. The investigational medicinal products (IMPs) will be taken orally.

Statistical Methods

Sample Size Estimation: A sample size of 174 subjects per group (total, 522 subjects) will provide at least 90% power to detect a change in the primary outcome measure (change from baseline in the MDS-UPDRS Parts II and III combined score) of 4 points, with a standard deviation of 9, 2-sided alpha level = 0.05, and assuming a 27% dropout rate.

In the event of higher than anticipated early terminations due to COVID-19 or other reasons, Cerevel may extend enrollment in order to maintain the planned statistical power.

Efficacy Analyses: The efficacy endpoints will be assessed for each of the 2 dose levels of tavapadon versus placebo. A hierarchical testing procedure with a prespecified order for the primary and key secondary endpoints will be used to control the Type I error rate at the 0.05 level (2-sided). Additional details will be provided in the statistical analysis plan.

The primary efficacy endpoint (the change from baseline to endpoint in the MDS-UPDRS Parts II and III combined score) will be analyzed using a Mixed Model for Repeated Measures (MMRM). The change from baseline at each postbaseline timepoint will be included in the MMRM as repeated measures. The baseline score will be included as a covariate, and treatment group, visit, the interaction between treatment group and visit, and the stratification factor (concurrent use of MAO-B inhibitor; yes/no) will be included as fixed factors. An unstructured covariance structure will be utilized. The difference between each tavapadon dose level and placebo at endpoint will be estimated based on the least square means (LSMeans) from the MMRM. A hypothetical strategy will be used to address intercurrent events (ICEs) of potential death, treatment discontinuations, missed visits/assessments, and start of prohibited concomitant medications. The data after treatment discontinuations or after the start of prohibited concomitant medications will be censored under the hypothetical strategy. The missing values are assumed to be missing at random (MAR) in the primary analysis, including missing due to COVID-19 control measures. Sensitivity analyses will be performed to assess the impact of deviation from MAR assumptions on the analysis results.

The key secondary endpoint of the change from baseline to endpoint in the MDS-UPDRS Part II score will be analyzed using an MMRM analysis similar to the analysis of the primary endpoint.

The key secondary endpoint of the percentage of responders at endpoint, defined as a score of “much improved” or “very much improved” on the Patient Global Impression of Change (PGIC), will be analyzed using the SAS® GLIMMIX procedure for binomial data with logit link. This generalized linear mixed model analysis will include response data from each postbaseline visit as repeated measures with treatment group, visit, and interaction between treatment group and visit as fixed effects. An unstructured covariance structure will be used for the repeated measures. If the model fails to converge with the

unstructured covariance structure, the heterogeneous Toeplitz structure or further reduced covariance structure may be used.

[figure not shown]
Other secondary endpoints (as listed in [Table 1](#)) will be analyzed similarly to the primary efficacy endpoint if the data are of a continuous nature, and similarly to the key secondary endpoint of percentage of responders on the PGIC at endpoint if the data are of ordered categorical nature.

Safety Analyses: Treatment-emergent adverse events (TEAEs) will be coded according to the Medical Dictionary for Regulatory Activities (MedDRA) and summarized by treatment group, system organ class, and preferred term. Additional summaries by seriousness, severity, relationship to IMP, and dose at the time of onset will also be prepared. Other safety endpoints (as listed in [Table 1](#)) will be summarized with descriptive statistics. Abuse potential will be assessed through active monitoring of events subject to additional monitoring (ESAM; ie, TEAEs related to abuse potential and TEAEs related to medication handling irregularities [MHIs]).

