3.2.3.1. Adverse Event of Special Interest (AESI)

For this study, any AEs related to abuse potential, AEs involving MHIs, abnormal liver function tests with a value $>3 \times$ ULN for ALT or AST and $>2 \times$ ULN for total bilirubin within the same visit, a value of $>3 \times$ ULN for ALT or AST and clinical jaundice, an AE leading to the discontinuation of IMP or from the study will be considered AESIs. These events will be noted by the investigator in the ADVERSE EVENTS eCRF.

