5.14.1. Adverse Events

Adverse events will be mapped to a Medical Dictionary for Regulatory Activities (MedDRA) version 27.0 or higher preferred term and system organ class. If a subject experiences multiple events that map to a single preferred term, the greatest severity and strongest investigator assessment of relation to IMP will be assigned to the preferred term for the appropriate summaries. Events with missing severity or relationship will be classified as outlined in [Section 3.2](#). Missing onset dates will be imputed as previously outlined in [Section 4.1](#) as required to determine treatment-emergent events.

Summaries of treatment-emergent AEs will include any AEs reported beginning with the initiation of study drug on Day 1 through end of reporting period specified in the protocol post the last dose of IMP. The occurrence of TEAEs will be summarized by treatment group using preferred terms, system organ classes, and severity. The TEAEs by subgroup of MAO-B inhibitor use will be summarized by treatment, organ class, and preferred term. Separate summaries of treatment-emergent serious adverse events (TESAEs), TEAEs related to IMP, AESIs (including AEs related to abuse potential and AEs involving medication handling irregularities), events leading to the discontinuation of IMP, and AESIs that did not result in discontinuation of IMP or study will be generated respectively. A summary of AEs by treatment phase and by dose at event onset will also be presented. Adverse events leading to the discontinuation of IMP by preferred term and phase at onset will be prepared. All adverse events reported will be listed for individual subjects showing both verbatim and preferred terms. All adverse events that occurred prior to the initiation of study treatment or after the protocol-specified reporting period post the last dose of IMP will be excluded from the summary tables but will be included in the listings.

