In addition, TEAEs rate per 100 person-years of exposure (PYE) will be summarized by treatment group using system organ class and preferred term. TEAEs with $\geq 2\%$ incidence in either tavapadon dose group and a greater incidence than the placebo group will be summarized by treatment group using preferred term in descending order of the incidence in the tavapadon 15 mg group followed by that in the tavapadon 5 mg group. The most common TEAEs, defined as an incidence $\geq 5\%$ in either tavapadon dose group and greater than 2 times of the incidence in the placebo group, will also be summarized by treatment group using preferred term in descending order of the incidence in the tavapadon 15 mg group followed by that in the tavapadon 5 mg group.

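### No grouped-term adverse event summary is planned for the hypotension, sleep and hallucination harms named in the rationale, so splitting across preferred terms can keep such a harm out of one or both threshold tables

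*Protocol*

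**What the plan says.** The rationale in Protocol 1.1, repeated in 2.1, describes the aim of "minimizing adverse events (AEs) that may be mechanistically linked to D2/D3 dopamine receptor agonists (notably, dose-limiting hypotension, impulse control disorders, sleep disorders", and the list ends with hallucinations, as a possibility only.

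The protocol plans TEAEs "summarized by treatment group, system organ class, and preferred term", and adds: "Additional summaries by seriousness, severity, relationship to IMP, and dose at the time of onset will also be prepared". SAP 5.14.1 gives the main table: "The occurrence of TEAEs will be summarized by treatment group using preferred terms, system organ classes, and severity". That table has no incidence cut-off. The same section adds separate summaries of serious, related and discontinuation-causing events, of AESIs, by treatment phase and by dose at onset; rates per 100 person-years; and a full listing with verbatim terms.

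Two further tables, both by preferred term, are filtered. One takes TEAEs with at least 2% "incidence in either tavapadon dose group and a greater incidence than the placebo group". The other, labelled the most common TEAEs, takes those with at least 5% "in either tavapadon dose group and greater than 2 times of the incidence in the placebo group".

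SAP 3.2.3.1 defines AESIs as "any AEs related to abuse potential, AEs involving MHIs, abnormal liver function tests" of a stated size, and events leading to discontinuation. Hypotension, sleep and hallucination events are not listed as AESIs in their own right. Neither document defines a grouped term, a standardised MedDRA query or any other pooled category for them.

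**The concern.** One clinical harm can be coded under more than one preferred term. A rule applied term by term then tests fragments of the harm, and each fragment can fall below a cut-off that the whole exceeds. The uncut table does not repair this. A subject may have several related terms, so adding rows does not give the number of subjects with at least one event. System organ class totals mix in unrelated events, and a listing makes no comparison between arms.

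This matters more for these harms than for an arbitrary one, because reducing them is part of the stated rationale and they are plausible in this trial. Protocol 2.3 reports dose-related falls in blood pressure with some asymptomatic hypotension, and counts sleep disorder among the most common events leading to discontinuation. Protocol 8.5 counts dizziness and abnormal dreams among the most common TEAEs. Protocol 2.2 links hallucinations with D2/D3-preferring agonists, particularly in the elderly, and this trial enrols up to age 80. A claim about such harms needs one count per harm per arm, and the plan does not provide it.

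**Working it through.** **Inputs.** Arm size 174 (Protocol 9.2). Cut-offs 2% and 5% per preferred term (SAP 5.14.1). The documents give no expected adverse event rate, no term split and no safety precision, so there is no planned safety figure to reproduce. Pooled incidence P and number of terms k are assumptions, shown as a range.

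**Step 1: subjects needed under one term.**
- 2% rule: 0.02 × 174 = 3.48, so 4 subjects (4/174 = 2.30%; 3/174 = 1.72%).
- 5% rule: 0.05 × 174 = 8.70, so 9 subjects (9/174 = 5.17%; 8/174 = 4.60%).

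**Step 2: what splitting can do.** Three related terms with 3 different subjects each are 1.72% each and enter neither table. Counted once as a group they are 9/174 = 5.17%, which passes both percentage cut-offs; the placebo conditions must also be met.

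**Step 3: how likely that is.** Split P evenly over k independent terms, so each has incidence p = P/k. With X ~ Binomial(174, p), the chance that no term reaches the cut-off is

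[P(X ≤ 3)]^k for the 2% table and [P(X ≤ 8)]^k for the 5% table.

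For P = 5% and k = 3, p = 1.67%:
- P(X ≤ 3) = 0.670, and 0.670³ = 0.30.
- P(X ≤ 8) = 0.997, and its cube, unrounded, is 0.992.

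Chance that no term reaches the cut-off, one arm (2% table / 5% table):

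| Pooled P | k = 1 | k = 2 | k = 3 | k = 4 |
|---|---|---|---|---|
| 3% | 23% / 92% | 54% / 99.7% | 73% / >99.9% | 84% / >99.9% |
| 5% | 2.4% / 49% | 13% / 94% | 30% / 99% | 46% / 99.8% |
| 6% | 0.6% / 28% | 5% / 85% | 16% / 97% | 29% / 99.5% |
| 8% | <0.1% / 6% | 0.6% / 54% | 3% / 87% | 9% / 97% |

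The k = 1 column is what chance alone does without splitting. The effect of splitting is the move away from that column.

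**Step 4: two features of the rule left out above.** A term enters a table if either dose group reaches the cut-off. If both doses had the same 5% harm split over three terms, the chance of missing would be 0.301² = 0.09 for the 2% table and 0.992² = 0.98 for the 5% table. If the harm sits mainly in one dose group, the one-arm figures are closer. The placebo conditions work the other way: they can only remove terms, so they make omission more likely.

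**The case against.** The strongest reply is that nothing is lost. The main tables, the person-year rates and the listings carry no cut-off, and the two filtered tables are additions. That is correct. A reader might infer that adverse events are tabulated only by single term, or that these harms could vanish from the report. The documents support neither. Protocol 8.4.6.1 plans a search across MedDRA terms, verbatim terms and free text for abuse-related events; its term list is in a separate plan not seen here and might include some psychiatric or sleep terms. Any event leading to discontinuation is an AESI.

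Second, two of the harms are measured independently of coding. SAP 5.14.6.1 counts subjects by arm and by phase with low supine pressures, falls from baseline and orthostatic drops, and vital signs are taken at every clinic visit. SAP 5.14.2 reports Epworth scores of 10 or more and 18 or more, and fits a repeated-measures model. Impulse control, the other harm in the rationale, has QUIP-RS with a model in SAP 5.14.3. This stands and narrows the point. It does not reach syncope or postural symptoms between visits, or sleep disorders other than daytime sleepiness. Nor does it reach hallucinations: the schedule of assessments has no dedicated instrument, and MDS-UPDRS Part I is analysed only as a total or within a combined score.

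Third, dramatic examples are easy to construct. A reader might imagine 15 subjects (8.6%) spread as 3 under each of five terms and absent from both tables. If 15 subjects fall at random over five equally likely terms, that exact split has probability 15!/(3!⁵ × 5¹⁵) = 0.6%. It should not be used as the expected size.

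**Conclusion.** The point holds as a reporting gap. SAP 5.14.1 defines no grouped-term summary for three kinds of harm named in the rationale and applies its 2% and 5% rules to single preferred terms. At a pooled incidence of 5% over three terms, the chance of missing rises from 2.4% to about 30% for the 2% table and from 49% to about 99% for the 5% table. These figures assume 174 subjects, an even split, independent terms and one arm, without the placebo conditions. They illustrate the mechanism and do not predict this trial. For the 2% table the problem fades as the harm becomes more common: 3% at a pooled incidence of 8% over three terms.

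The gap is clearest for hallucinations or psychosis, then for symptomatic hypotension or syncope between visits and for sleep disorders other than daytime sleepiness. A reader might go further and infer that absence from the filtered tables would be taken as evidence for the drug's claimed advantage. Nothing in the documents says those tables will be used that way. No planned analysis is invalid and the primary result is untouched. This is a cheap improvement.

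**What to change.** In SAP 5.14.1, before unblinding, fix preferred-term lists or standardised MedDRA queries for three groups: hypotension and syncope; somnolence and sleep disorders; hallucinations and psychosis. For each group, tabulate by arm the subjects with at least one TEAE, counting each subject once, with the difference from placebo and its 95% confidence interval. Apply the 2% and 5% rules to these groups as well as to single terms.

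The multi-term search for abuse-related events is a precedent within the same protocol. The SAP already plans reviews before database lock and unblinding (5.9.3.4 for missing-data cases, 5.16 for protocol deviations), so the term lists can be settled then. No new data are needed. The cost is one table and a short blinded review to agree the terms.
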